Objectives:	Alternative Hypothesis: Frequency and intensity of adverse events among pediatric patients with apophysitis of the knee who receive iontophoresis with DSP and PT will be different from those who receive iontophoresis with placebo or PT alone. Primary Objective:
	 To compare the functional outcomes of iontophoresis with DSP in combination with PT versus iontophoresis with placebo in combination with PT versus PT alone in pediatric patients diagnosed with apophysitis of the knee.
	Secondary Objectives:
	 To compare the patient reported outcomes of iontophoresis with DSP in combination with PT versus iontophoresis with placebo in combination with PT versus PT alone in pediatric patients diagnosed with apophysitis of the knee.
	 To compare the safety of iontophoresis with DSP in combination with PT versus iontophoresis with placebo in combination with PT versus PT treatment alone in pediatric patients diagnosed with apophysitis of the knee.
Endpoints:	Primary Endpoint:
	- Length of time to meet RTS criteria as measured in days Secondary Endpoints:
	 Percent difficulty with activities as measured by the LEFS
	 Patient reported activity as measured by the Godin Leisure-Time Activity Questionnaire
	 Patient reported pain as measured by the FACES Pain Scale
	 Safety as measured by number and intensity of iontophoresis or DSP- related adverse events
Study Population:	147 pediatric patients referred by the Children's Hospital of the King's Daughters (CHKD) Primary Care Sports Medicine Physicians and Orthopedic Physicians to the CHKD Sports Medicine PT Department, with a diagnosis of apophysitis of the knee.
Phase:	II
Description of	Participants will be screened, enrolled, and treated at six (6) CHKD Sports

Sites/Facilities Enrolling Participants:	Medicine PT Clinics across the Hampton Roads area.

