To compare the patient reported outcomes of iontophoresis with DSP in combination with PT versus iontophoresis with placebo in combination with PT versus PT alone in pediatric patients diagnosed with apophysitis of the knee.

To compare the safety of iontophoresis with DSP in combination with PT versus iontophoresis with placebo in combination with PT versus PT treatment alone in pediatric patients diagnosed with apophysitis of the knee.

Secondary Endpoints

- Patient reported percent difficulty with activities as measured by the LEFS
- Patient reported pain as measured by the FACES Pain Scale
- Patient reported activity as measured by the Godin Leisure-Time Activity Questionnaire
- Safety as measured by number and intensity of iontophoresis or DSP-related adverse events

Justification for Endpoints

- The LEFS is a validated patient reported outcome tool that assesses the patient's ability to perform 20 different activities involving the lower extremity. It allows the patient to rate his/her level of difficulty with each task as a result of pain or impairments to the involved lower extremity. The LEFS was selected based on its ease of administration and its inclusion of both common Activities of Daily Living (ADL's) and more advanced sport-specific activities.
- The FACES Pain Scale allows the pediatric patient to select the face that best represents his/her pain intensity. This is assumed to generate a more accurate pain rating than a quantitative estimation required with a numerical rating scale, where children may not all have a good understanding of the quantitative value of numbers. It has been documented that children prefer the FACES Scale to the Visual Analog Scale, which would require them to select a point on a horizontal line to indicate pain intensity. Using the FACES Pain Scale will allow Treating Therapists to track the patients' subjective pain ratings throughout the rehabilitation process.
- The Godin Leisure-Time Activity Questionnaire is a patient reported outcome tool that quantifies the patient's level of strenuous, moderate, and mild physical activity in a typical week. This provides the Treating Therapists with quantitative information regarding the

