patient's typical level of physical activity prior to the onset of knee apophysitis to facilitate a full return to prior level of function following completion of physical therapy. The Godin Leisure-Time Activity Questionnaire was selected based of its inclusion of low, moderate, and high level physical activities with examples for each category for ease of completion by patient/parent.

• Tracking the number and intensity of adverse events (see Section 8.3.3.1 Definition of Adverse Events) will determine if iontophoresis with DSP is a safe treatment option for this population by providing quantitative and qualitative data.

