6.3 MEASURES TO MINIMIZE BIAS: RANDOMIZATION AND BLINDING

A center-stratified randomization method will be used to maintain balance between treatment groups and centers. Equal number of participants per intervention will be considered to maximize study power. The CHKD Pharmacy Department will hold the randomization key and will prepare bottles of study drug and placebo (see Section 6.2.2 Formulation, Appearance, Packaging, and Labeling).

Treating therapists will assign randomization codes in chronological order as participants enroll in the study. Since the study drug and sodium chloride are identical in appearance, the Treating Therapists will

be blinded to study assignment. Those participants assigned to "Group C", or standard PT alone, will be unblinded to treatment as they will not receive iontophoresis.

In the case of an unexpected and serious adverse event in which knowing the study assignment is critical to the medical care of the participant, the CHKD pharmacist may release this information to the Independent Safety Monitor only, who may share this information with the treating physician.

Both the Treating Therapist and the participants assigned to one of the two iontophoresis groups will be blinded to study treatment. The DSP injection and 0.9% sodium chloride injection are clear, colorless liquids that will be supplied by the CHKD Pharmacy Department in identical looking single-use bottles. Each bottle will contain 1.8 mL of solution and will be labeled in a blinded fashion as either lontophoresis Study Drug "A" or "B".

In this study, the Treating Therapists will also perform all physical therapy assessments. While having a separate group of "assessing therapists" and "treating therapists" minimizes bias even further than the current study design, combining their roles is preferred as it reduces error by minimizing the number of therapists involved, improves completion consistency of the RTS Criteria Checklist, and minimizes scheduling conflicts caused when trying to coordinate two therapist's schedules for every study visit conducted.

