8.3.3.2 RELATIONSHIP TO STUDY INTERVENTION

All adverse events (AEs) will have their relationship to study intervention assessed by the Treating Therapist who examined and evaluated the participant based on temporal relationship and his/her clinical judgment. The degree of certainty about causality will be graded using the categories below:

- **Related** The AE is known to occur with the study intervention, there is a reasonable possibility that the study intervention caused the AE, or there is a temporal relationship between the study intervention and event. Reasonable possibility means that there is evidence to suggest a causal relationship between the study intervention and the AE.
- Not Related There is not a reasonable possibility that the administration of the study intervention caused the event, there is no temporal relationship between the study intervention and event onset, or an alternate etiology has been established.

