9 STATISTICAL CONSIDERATIONS

9.1 STATISTICAL HYPOTHESES

• Primary Efficacy Endpoint(s):

Length of time to meet RTS criteria as measured in days

Null Hypothesis: Time to achieve RTS criteria for Pediatric patients with apophysitis of the knee who receive iontophoresis with DSP and PT is the same as those who receive iontophoresis with placebo and PT or PT alone.

Alternative Hypothesis: Time to achieve RTS criteria for Pediatric patients with apophysitis of the knee who receive iontophoresis with DSP and PT will be different from those who receive iontophoresis with placebo and PT or PT alone.

• Secondary Endpoint(s):

Efficacy: Patient reported outcomes:

Null Hypothesis: There is not any significant difference in patient reported outcomes (LEFS, FACES pain scale, and Godin Leisure-Time Exercise) between pediatric patients with apophysitis of the knee who receive iontophoresis with DSP and PT and those who receive iontophoresis with placebo and PT or PT alone.

Alternative Hypothesis: Patient reported outcomes (LEFS, FACES pain scale, and Godin Leisure-Time Exercise) of pediatric patients with apophysitis of the knee who receive iontophoresis with DSP and PT will be different from those who receive iontophoresis with placebo and or PT alone.

Safety: Frequency and intensity of adverse events

Null Hypothesis: There is not any significant difference in frequency and intensity of adverse events between pediatric patients with apophysitis of the knee who receive iontophoresis with DSP and PT and those who receive iontophoresis with placebo and PT or PT alone.

Alternative Hypothesis: Frequency and intensity of adverse event among pediatric patients with apophysitis of the knee who receive iontophoresis with DSP and PT will be different from those who receive iontophoresis with placebo and PT or PT alone.

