9.4.4 SAFETY ANALYSES

A GEE model will be conducted to estimate likelihood of occurring and intensity of adverse events for Pediatric patients with apophysitis of the knee who receive iontophoresis with DSP treatment and PT as compared to those who receive placebo or PT alone.

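### The safety endpoint counts only iontophoresis- or DSP-related events, which PT alone cannot have, while the hypotheses and model refer to all adverse events; the plan does not say which governs

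*Combined protocol and SAP*

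**What the plan says.** **Endpoint.** Section 3 gives the secondary safety endpoint as "Safety as measured by number and intensity of iontophoresis or DSP-related adverse events". The synopsis (Section 1.1) carries the same restriction.

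**Objective.** Section 3 sets out "To compare the safety of iontophoresis with DSP in combination with PT versus iontophoresis with placebo in combination with PT versus PT treatment alone". PT alone is therefore one of the comparators. Section 6.3 says that Group C participants "will be unblinded to treatment as they will not receive iontophoresis".

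**Justification, hypothesis and model.** These drop the restriction:
- The justification in Section 3 begins "Tracking the number and intensity of adverse events".
- The null hypothesis in Section 9.1 reads "There is not any significant difference in frequency and intensity of adverse events between pediatric patients with apophysitis of the knee", and goes on to set DSP against placebo or PT alone.
- Section 9.4.4 states "A GEE model will be conducted to estimate likelihood of occurring and intensity of adverse events", for DSP compared with placebo or PT alone. It gives no link function or distribution.

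**Relatedness.** Under Section 8.3.3.2 the Treating Therapist judges relatedness. One of the alternatives that make an event Related is "or there is a temporal relationship between the study intervention and event". The same section allows Not Related where causation is not reasonably possible, where there is no temporal relationship, or where another cause has been established.

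**Collection and use.** Section 8.3.4 has every adverse event on study documented, whatever its relationship. Section 9.4.7 makes the safety outcome one of the two whose interim result can lead the Independent Safety Monitor to inform the investigator and consider early termination.

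**The concern.** An event cannot be related to iontophoresis or DSP in a child who receives neither. On the endpoint as defined, the PT-alone count is fixed at zero before the trial starts, and that arm gives no information on how often such events would be reported without a patch. If the GEE uses a logit link, an arm with no events has no finite odds ratio.

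The relatedness label is also not neutral between the arms. Timing alone can be enough for Related, and the therapist who decides knows who is in Group C. A minor background event during treatment could count in an iontophoresis arm but could not count in PT alone.

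At stake is what a reported difference from PT alone would mean, in a trial that intends its adverse event data to show whether the treatment is safe in children. Because the plan contains two versions of the outcome, the choice could be made after data have been seen, and the chosen version could reach the interim review.

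**Working it through.** **1. The plan's own figure.** Section 9.2 gives 108 participants as the requirement for the safety hypothesis. No event rate, effect size or test is stated, so 108 cannot be reproduced, and it does not show which version of the outcome was in mind.

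**2. The passages side by side.**

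| Place | Events counted | Arms |
|---|---|---|
| Synopsis and Section 3, endpoint | Iontophoresis- or DSP-related only | Not stated |
| Synopsis and Section 3, objective | Safety in general | DSP, placebo, PT alone |
| Section 3, justification | Adverse events | Not stated |
| Synopsis and Section 9.1, hypotheses | Adverse events | DSP against placebo or PT alone |
| Section 9.4.4, GEE | Adverse events | DSP against placebo or PT alone |
| Section 8.3.4, collection | All, whatever the relationship | All |

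The related-only restriction appears only in the two endpoint definitions.

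**3. What the related-only version does against PT alone.**

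Inputs: 49 per group (Section 9.2); two-sided 0.05 (Section 9.4.1); zero events in PT alone (follows from the definition). The rate *p* of participants in the DSP arm with a related-labelled event is an assumption, because the documents give none. Section 2.3.3 reports no significant reaction in over 23,000 past treatments, but that does not bound the rate of mild local events.

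Smallest significant result, by Fisher's exact test:
- 5 of 49 versus 0 of 49: p = 0.056
- 6 of 49 (12.2%) versus 0 of 49: p = 0.027

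Six events are therefore needed. The chance of significance is P(X ≥ 6) with X ~ Binomial(49, *p*). The same threshold of six applies at 42 per group (126/3, the number before the non-compliance allowance), where p = 0.026.

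| Assumed *p* | 49 per group | 42 per group |
|---|---|---|
| 3% | 0.3% | 0.2% |
| 5% | 3.5% | 1.7% |
| 7.5% | 15.9% | 9.2% |
| 10% | 36.5% | 24.0% |
| 15% | 76.4% | 61.7% |
| 20% | 94.5% | 87.1% |

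Fisher's test stands in for the planned GEE and is conservative. A simulated Pearson chi-square for DSP versus PT alone (49 per group, 40,000 runs) gave 23% at 5% and 73% at 10%.

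**4. Which contrasts are affected.** With equal rates in DSP and placebo and zero in PT alone, a simulated three-arm Pearson chi-square rejected in 16% of runs at 5%, 62% at 10% and 94% at 15%. DSP versus placebo rejected in about 5% to 6% at the same rates, so that contrast is not distorted.

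**5. Effect of counting all events.** With the same true rate in all three arms (10% to 30%), the three-arm test rejected in about 5% of runs, as it should.

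**The case against.** The strongest reply is that the comparison to be tested is already the right one. The hypotheses and the GEE are written for adverse events without restriction, and the data for all three arms are collected. This stands, and it rules out two readings that a reader might infer. One is that the planned three-arm comparison is built to show a difference: only the endpoint definition has that property, and the hypotheses and the model do not repeat it. The other is that the safety objective against PT alone cannot be answered: it can be, from data the plan already gathers. The reply does not settle which version governs.

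Second, a reader might infer from Section 8.3.3.2 that every background event in the iontophoresis arms would be counted as related. The documents do not support that. The section calls for clinical judgement and lets an event with an established other cause be Not Related. What remains is a risk of differential labelling of unknown size.

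Third, a difference from PT alone need not be an artefact. Section 2.3.1.1 lists redness, dryness, discolouration and, rarely, burns at the application site. These are caused by the treatment and are properly absent without a patch. Only misattributed background events would be artefact, and the related-only endpoint cannot separate the two.

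Fourth, the larger percentages above depend on the assumed rate. If a third of a 15% background rate were labelled related (0.15 × 1/3 = 5%), the Fisher figure would be 3.5%, not 76%.

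**Conclusion.** The endpoint definition and the analysis disagree. On the definition, PT alone is zero by construction and cannot serve as a fair comparator; on the analysis wording, the comparison is sound but departs from the stated endpoint. This needs correction because the safety outcome also feeds the interim decision in Section 9.4.7, although that decision remains a matter of the monitor's judgement.

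For the related-only version, the chance of a significant difference from PT alone runs from 0.3% at an assumed labelled rate of 3% to 95% at 20%. These figures rest on 49 per group, Fisher's test in place of the GEE, and rates that the documents do not supply. They show how strongly the result depends on labelling, not how often it would be wrong. The point concerns one contrast of a secondary endpoint: the primary endpoint and the blinded DSP versus placebo safety contrast are untouched.

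**What to change.** 1. In the synopsis and Section 3, define the comparative safety endpoint as the number and intensity of all adverse events after the first study treatment visit, whatever their relatedness, compared across the three arms. This matches Sections 9.1 and 9.4.4. Anchoring it to the visit also gives PT alone a clear start. Section 9.3 defines the analysis set by receipt of a dose, so the plan should state that Group C belongs to the safety set.
2. Limit the formal comparison of related events to DSP versus placebo iontophoresis, where relatedness is judged blind to the solution.
3. In Section 9.4.4 state the link and distribution, and in Section 9.4.7 say that the safety outcome is the all-event version.

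The cost is wording in the protocol and analysis plan. Section 8.3.4 already requires every event to be recorded, so no new data, visits or participants are needed. The change should be made before any further interim review of safety by group.

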2.3.3 ASSESSMENT OF POTENTIAL RISKS AND BENEFITS

The systemic administration of steroids such as dexamethasone is associated with side effects that can affect multiple organ systems in the body including the muscular system, skeletal system, immune system, renal system, digestive system, integumentary system, nervous system, endocrine system, and circulatory system. Since dexamethasone will be administered transdermally in this study and for a short duration of time, we do not expect to see the systemic side effects of the medication. We have minimized the risk to the participants by administering DSP transdermally. The side effects of most concern would be local cutaneous reactions or hypersensitivity reactions.

The benefits of facilitating a quicker recovery from knee apophysitis to allow both the physical and psychosocial benefits previously described far outweigh any small mostly theoretical risk. Any local reaction that could occur is self-limited in time and morbidity. In our almost 20 years in clinical experience of using iontophoresis with DSP we have never seen any significant adverse reaction. However, we have seen thousands of patients improve quickly with the addition of iontophoresis with DSP. From 2009 (the year data collection started) to 2018, the CHKD Sports Medicine PT program has administered over 23,000 iontophoresis with DSP treatments and none have resulted in a significant adverse reaction. Currently there are no published studies documenting this perceived clinical benefit and it is imperative to determine if it is better than the current home regimen. Outside of the benefits to the individual patient there are also benefits to the parent/ guardian of the minor child by minimizing their time lost from work. This in turn will have societal benefits (psychosocially and economically).

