9.2 SAMPLE SIZE DETERMINATION

To assess the primary variable of interest, a power analysis indicated that a total sample of 126 participants would be required to detect medium effects (f = 0.28) with 80% power and $\alpha = 0.05$ using Generalized Linear Model (GLM).

The required sample size to test secondary hypotheses was calculated as 87 and 108 participants for patient reported outcomes and safety, respectively. Therefore, a total sample of 126 participants provides sufficient power for testing secondary hypotheses.

Given an estimated 15% non-compliance rate, the sample size will be increased by 15%, for a total sample size of 147 participants (49 per group).

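### The plan says adverse event tracking will determine whether DSP iontophoresis is safe, but a no-difference test with 42 to 49 children per arm and no stated event rate cannot support that conclusion

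*Combined protocol and SAP*

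**What the plan says.** - **Section 3, justification of the safety endpoint:** tracking the number and intensity of adverse events "will determine if iontophoresis with DSP is a safe treatment option for this population by providing quantitative and qualitative data". The endpoint counts events related to iontophoresis or to DSP, at every severity.
- **Section 9.1:** the safety null is no difference in frequency and intensity between DSP and the two comparators. There is no margin and no acceptable rate.
- **Section 9.2:** the primary calculation is that "a total sample of 126 participants would be required to detect medium effects (f = 0.28) with 80% power". The secondary requirements were "calculated as 87 and 108 participants for patient reported outcomes and safety, respectively", and so "a total sample of 126 participants provides sufficient power for testing secondary hypotheses". No event rate, effect size or test is given for the 108. Enrolment is then raised to 147, 49 per arm.
- **Section 9.4.4:** "A GEE model will be conducted to estimate likelihood of occurring and intensity of adverse events". No confidence interval is mentioned, whereas section 9.4.3 promises 95% intervals for the patient-reported outcomes.
- **Section 2.3.3:** the department "has administered over 23,000 iontophoresis with DSP treatments and none have resulted in a significant adverse reaction". Section 2.3.1.1 describes rash, irritation and burns as rare.

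**The concern.** A test of no difference can show harm when it rejects. It cannot show safety when it does not reject, least of all with few events. The plan pairs such a test with an assurance of sufficient power and a promise to settle whether the treatment is safe, and nothing in the analysis section links the two.

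The treatment is a steroid given to children by a route that section 2.3.1.2 says is not FDA-approved and has no published data on systemic effects. The final report could therefore carry a safety conclusion that the data cannot bear. What the design can deliver is an upper limit on risk, and the plan does not ask for one.

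**Working it through.** **Inputs.** From section 9.2: 126 needed (126/3 = 42 per arm), 147 enrolled (49 per arm), 108 for safety. From section 9.4.1: two-sided 0.05. The placebo event rate is not stated. I take 0% as the case most favourable to the plan, and 5% as an alternative. Both are assumptions.

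**1. The plan's own figures.** A one-way F test with three groups, f = 0.28 and noncentrality f²N has power 0.790 at 123 and 0.800 at 126, so 126 reproduces. For inflation, 126 × 1.15 = 144.9 and 126/0.85 = 148.2; 147 lies between them.

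The 108 has no stated inputs, and at least two routes reach it:
- a 2-df chi-square with w = 0.30: power 0.7998 at 107 and 0.804 at 108;
- a three-group repeated-measures F test (between-group factor, f = 0.25, 3 measurements, correlation 0.5): power 0.797 at 105 and 0.809 at 108. The same route with f = 0.28 gives 87, the other secondary figure (0.795 at 84, 0.810 at 87).

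The basis of 108 therefore cannot be recovered from the document.

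**2. Smallest significant split, DSP against placebo, 49 per arm.** By Fisher's test, 5 against 0 gives p = 0.056 and 6 against 0 gives p = 0.027. At 42 per arm the threshold is also 6 against 0. The uncorrected chi-square rejects from 4 against 0 (p = 0.041; 3 against 0 gives 0.079).

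**3. DSP rate needed for 80% power, placebo rate 0%.** For the two exact calculations, power is P(X ≥ c | n, p), with c = 6 (Fisher) or c = 4 (chi-square). The pooled normal approximation is Φ{[p − 1.96√(2p̄(1−p̄)/n)] / √(p(1−p)/n)}, with p̄ = p/2. At n = 49 and p = 0.145 this is (0.145 − 0.103)/0.0503 = 0.84, and Φ(0.84) = 0.80. The unpooled version solves p/√(p(1−p)/n) = 2.80.

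| Method | 49 per arm | 42 per arm |
|---|---|---|
| Uncorrected chi-square, exact power | 11.0% | 12.7% |
| Unpooled normal | 13.8% | – |
| Pooled normal | 14.5% | 16.7% |
| Fisher | 15.7% | 18.2% |

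With a 5% placebo rate and 49 per arm, the DSP rate needed is 25.0% (pooled normal) or 26.7% (Fisher).

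A three-arm 2-df chi-square, with 0% in both comparators, reaches 80% power at 9.5% with 49 per arm. Part of that gain comes from the PT-alone arm, where events related to iontophoresis or DSP can hardly occur by definition. DSP against placebo iontophoresis is the comparison that isolates the drug.

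**4. Power for less common events, placebo rate 0%.**
- True DSP risk 5%, 49 per arm: P(X ≥ 6) = 3.5% (Fisher), P(X ≥ 4) = 23% (uncorrected chi-square), 35% (pooled normal, which is rough with so few events). Fisher at 42 per arm: 1.7%.
- True DSP risk 10%, Fisher: 37% at 49 per arm, 24% at 42.

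**5. What zero events would show.** With 0/49 the upper limit is 1 − 0.05^(1/49) = 5.9% (one-sided 95%) or 1 − 0.025^(1/49) = 7.3% (two-sided). With 0/42 it is 6.9% or 8.4%.

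**6. Seeing an event is not the same as comparing arms.** The chance of at least one case among 49 children is 1 − 0.95^49 = 92% at a 5% risk and 39% at a 1% risk. The trial may well reveal such events. It can seldom show them as a between-arm difference.

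**The case against.** The strongest reply has four parts.

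**The plan never says that a non-significant result will be read as safety.** This is correct. A reader might infer it from sections 3, 9.1 and 9.2 together, but it is not stated. Section 3 speaks of quantitative and qualitative data, and section 9.4.4 of estimation. Section 9.4.1 gives frequencies and percentages, and an Independent Safety Monitor reviews cumulative events (sections 8.3.5 and 10.1.5). That review protects participants during the trial. Neither it nor the frequencies supply an interval or a rule for the final conclusion.

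**The calculations above are not the planned analysis.** A GEE on repeated visits may have more power for frequent local reactions such as redness. The placebo arm receives the same current, so its rate of such reactions need not be near zero. Both points stand. The first does not help with uncommon events such as burns, and the second raises the DSP rate needed.

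**The basis of 108 is unknown.** With w = 0.30 and no comparator events, the DSP rate would be 12.9%, and a reader might conclude that the sponsor planned for 13% against 0%, or that the trial detects events affecting one child in eight. The documents support neither. The value of w is inferred, another route also gives 108, and 12.9% against 0% has 62% power by Fisher's test at 49 per arm.

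**The 23,000-treatment record concerns significant reactions, whereas section 9.2 refers to all adverse events.** This also stands. The record does not prove the power statement false. It shows that the reactions of most concern are too rare for this trial to compare.

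**Conclusion.** The concern holds, as an unsupported safety conclusion rather than a false calculation. The claim in section 3 goes beyond what 42 to 49 children per arm and a no-difference test can deliver. The power statement in section 9.2 has no stated basis and is unsupported for uncommon events. It may be reasonable for common ones, and the document does not allow a check.

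In size, 80% power for a pairwise difference needs roughly 11% to 16% of DSP children affected if placebo has none, and about 25% to 27% if placebo has 5%. An empty DSP arm of 49 rules out only risks above about 6% to 7%. The first two results rest on assumed placebo rates and on one yes/no outcome per child. The last needs neither a comparator rate nor a model.

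**What to change.** 1. **Section 3:** replace the statement that tracking will determine whether the treatment is safe with: *will describe and compare adverse events*.
2. **Section 9.2:** state the event rates or effect size, the test and any repeated-measures assumptions that produced 108, and limit the power statement to common adverse events; or delete it for safety. Do not insert 13% against 0% as the basis unless the sponsor confirms it.
3. **Section 9.4.4:** base the safety conclusion on the number and percentage of children with an event in each arm, by severity, with exact 95% confidence intervals, and on the DSP-minus-placebo risk difference with its 95% interval. Keep the GEE as supportive. Add: *a non-significant difference will not be taken as evidence of safety*.

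The cost is wording and a few simple tables. No change to sample size, visits or data collection is needed. The drawback for the sponsor is a less favourable safety claim.
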